8. SAFETY AND TOLERABILITY

Appendix A provides a list of data displays. Sample data displays are included in a separate document.

8.1. General Considerations

Safety analyses will be conducted for the SAF. No formal statistical testing will be performed. Summary tables may be replaced with listings when appropriate. For instance, an AE frequency table may be replaced with a listing if it only contains a few unique PTs reported on relatively few participants.

All TEAEs, clinical laboratory measurements, and vital sign measurements will be summarized by treatment group for the FL, MZL, and overall populations. Quantitative safety variables and their changes from baseline (laboratory and vital signs) will be summarized with descriptive statistics. Abnormal values outside of established ranges will be flagged and tabulated based on predefined criteria.

8.2. Adverse Events

8.2.1. Adverse Event Definitions

A TEAE is any AE either reported for the first time or worsening of a pre-existing event on or after the first dose of study treatment until 90 days after the last dose of study treatment. Analysis of AEs (as discussed below) will be limited to TEAEs, but data listings will include all AEs regardless of their timing in relation to study treatment administration. For the purposes of analysis, all AEs will be considered TEAEs unless the AE can unequivocally be defined as not treatment-emergent.

Adverse events will be tabulated by MedDRA PT and SOC. Severity of AEs will be graded using the NCI CTCAE v5. The CTCAE reporting guidelines and grading details are available on the Cancer Therapy Evaluation Program website.

The subset of AEs considered by the INV to be related to study drug will be considered to be treatment-related AEs. If the INV does not specify the relationship of the AE to study drug, the AE will be considered to be treatment-related. The incidence of AEs and treatment-related AEs will be tabulated. In addition, serious TEAEs will also be tabulated.

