8.3. Safety Assessments

Planned timepoints for all safety assessments are provided in Table 3 and Table 4.

The investigator(s) and the sponsor will review the safety data.

Safety will be evaluated by monitoring all AEs and clinically significant abnormalities identified through physical examinations, vital signs, and laboratory assessments. Such events and laboratory and AE toxicities will be graded according to NCI CTCAE v5.0 (or higher). Laboratory safety assessments will include routine monitoring of hematology and blood chemistry and tests of immunologic parameters.

Adverse events, pregnancies, concomitant medications, procedures, and hospitalizations will be recorded from signing the ICF until 90 days after the last dose of treatment or until the start of new anticancer therapy, whichever occurs first. Participants who relapse or progress and/or

prematurely discontinue the study treatment will continue to be followed for SPM throughout the study.

Adverse events and concomitant medications terms will be coded using MedDRA and a validated medication dictionary.

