9.4. Reporting of Serious Adverse Events

Regardless of suspected causality (eg, relationship to study treatment or study procedure[s]), all SAEs occurring after the participant has signed the ICF through completion of the study *or* until the participant starts a new anticancer therapy (whichever occurs earlier) must be reported to the sponsor (or designee) within **24 hours** of learning of its occurrence, unless otherwise specified by the Protocol. The investigator will submit any updated SAE data to the sponsor (or designee) immediately, without undue delay but not later than within 24 hours of it being available. For Japan, this information must also be reported immediately to the head of the study site in Japan.

Investigators are not obligated to actively seek SAE information after the EOT visit. If the investigator learns of any SAE, including a death, at any time during this period, and he/she considers the event to be reasonably related to the study treatment or study participation, then the investigator must notify the sponsor (or designee) within 24 hours of becoming aware of the event.

After the initial AE/SAE report, the investigator is required to proactively follow each participant at subsequent visits/contacts. All SAEs and AESIs (as defined in Section 9.5.1) will be followed until resolution, stabilization, the event is otherwise explained, or the participant is lost to follow-up (as defined in Section 7.3).

Prompt notification by the investigator to the sponsor regarding an SAE is essential so that legal obligations and ethical responsibilities towards the safety of participants and the safety of a study treatment under clinical investigation are met.

If the SAE is not documented in the RSI of the IB or product information for study treatment (new occurrence) or marketed products, respectively, and is thought to be related to the study treatment, the sponsor or its designee may urgently require further information from the investigator for expedited reporting to health authorities. The sponsor or its designee may need to issue an Investigator Notification to inform all investigators involved in any study with the same drug that this SAE has been reported. SUSARs will be collected and reported to the competent authorities and relevant ethics committees in accordance with Directive 2001/20/EC or as per national regulatory requirements in participating countries.

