7.3.2.3. Overall Survival in the Follicular Lymphoma Population

Overall survival is defined as the time from randomization until death from any cause. All participants should be followed until death or until the end of study, whichever comes first, as specified in the Protocol.

The cause of death ("disease progression," "adverse event," or "other") will be summarized.

Participants who are not reported as a death at the time of the analysis cutoff will be censored at the earlier of the analysis cutoff and date of last known alive. The last known alive date is defined as the later of the last study visit and the date the participant was last known alive from the "Survival Follow-Up," "End of Treatment," and "End of Study" eCRFs. Partial death dates will be handled using the rules described in Section 4.1.4.

Overall survival will be compared and analyzed using stratified tests as described in Section 7.3 for PFS with FL in the FAS at the time of interim, primary, and final analysis. Participants will be censored at the last date they were known to be alive, regardless if a new antilymphoma therapy was started.

Post-treatment systemic antilymphoma therapies will be summarized and listed.

[figure not shown]

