8.2.2. Adverse Events of Special Interest by eCRF

The number (%) of participants who had an AESI, the time to onset of each AESI, and the longest duration of each AESI will be summarized by treatment group.

Whether an AE is an AESI and which AESI it is can be found in the "Adverse Event" eCRF form. This information will be used to identify AESIs.

Adverse events of special interest for tafasitamab/placebo include TLS, IRRs and allergic reactions to study drug ≥ Grade 3, CRS, SPMs, hepatitis B reactivation, and PML.

Adverse events of special interest for lenalidomide include SPMs.

The longest duration of an AESI is defined as the longest interval between the date of occurrence of an AESI and the date of resolution. If participants have a missing or partial onset/end date of an AESI, the partial or missing dates will be handled using the rules explained in Section 4.1.4. Participants who have a missing end date of an AESI at the time of analysis will be right-censored using the following algorithm:

- If the AESI is serious, then the participant will be censored at the earlier date of data cutoff, study discontinuation, or death.
- If the AESI is not serious,
 - If the participant is ongoing with study treatment, then the participant will be censored at the data cutoff date.
 - If the participant discontinued treatment, then the participant will be censored at date of safety follow-up visit, or 90 days after the EOT visit (or after the last dose if the EOT visit was not performed), whichever is later; the censored date will be truncated by the earlier date of data cutoff, study discontinuation, or death if beyond.

The Kaplan-Meier estimate of median time to resolution/improvement and its 95% CIs will be provided, with the CIs calculated using the generalization of Brookmeyer and Crowley's method (1982) with log-log transformation (Klein and Moeschberger 1997). Resolution/improvement rates at selected timepoints will also be provided with 95% CIs calculated using Greenwood's formula to estimate the standard error. Such analysis for an AESI will not be conducted if 10 or fewer participants had the AESI.

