3.2.22.x	Summary of Lenalidomide Treatment- Related Serious Treatment-Emergent Adverse Events by MedDRA SOC and Preferred Term	SAF	X	X	X		X	X

Table No.	Title	Pop	FL	MZL	Overall	Jap FL	Jap Overall	Standard
3.2.23.x	Summary of Rituximab Treatment- Related Serious Treatment-Emergent Adverse Events by MedDRA SOC and Preferred Term	SAF	X	X	X		X	X
3.2.24.x	Summary of Treatment-Emergent Adverse Events With a Fatal Outcome by MedDRA SOC and Preferred Term	SAF	X	X	X		X	X
3.2.25.x	Summary of Treatment-Emergent Adverse Events Leading to Lenalidomide Dose Modification by MedDRA SOC and Preferred Term	SAF	X	X	X		X	X
3.2.26.x	Summary of Treatment-Emergent Adverse Events Leading to Tafasitamab/Placebo Dose Modification by MedDRA SOC and Preferred Term	SAF	X	X	X		X	X
3.2.27.x	Summary of Treatment-Emergent Adverse Events Leading to Rituximab Dose Modification by MedDRA SOC and Preferred Term	SAF	X	X	X		X	X
3.2.28.x	Summary of Treatment-Emergent Adverse Events Leading to Discontinuation of Tafasitamab/Placebo by MedDRA SOC and Preferred Term	SAF	X	X	X		X	X
3.2.29.x	Summary of Treatment-Emergent Adverse Events Leading to Discontinuation of Lenalidomide by MedDRA SOC and Preferred Term	SAF	X	X	X		X	X
3.2.30.x	Summary of Treatment-Emergent Adverse Events Leading to Discontinuation of Rituximab by MedDRA SOC and Preferred Term	SAF	X	X	X		X	X
3.2.31.x	Summary of Treatment-Emergent Adverse Events of Special Interest (eCRF) by Category, Preferred Term, and Maximum Severity	SAF	X	X	X		X	X
3.2.32.x	Summary of Time to Onset and Longest Duration of Treatment-Emergent Adverse Events of Special Interest (eCRF)	SAF	X	X	X		X	
3.2.33.x	Summary of Treatment-Emergent Adverse Events of Special Interest by AESI Category, Preferred Term, and Maximum Severity	SAF	X	X	X		X	X
3.2.34.x	Summary of Time to Onset and Longest Duration of Treatment-Emergent Adverse Events of Special Interest	SAF	X	X	X		X	
3.2.35.x	Summary of Grade 3 or 4 Selected Hematological Treatment-Emergent Adverse Events	SAF	X	X	X		X	X
3.2.36.x	Summary of Fatal Selected Hematological Treatment-Emergent Adverse Events	SAF	X	X	X		X	X
3.2.37.x	Summary of Duration of Treatment-Emergent Adverse Events of the Selected Preferred Terms and Customized MedDRA Queries	SAF	X	X	X		X	

Table No.	Title	Pop	FL	MZL	Overall	Jap FL	Jap Overall	Standard
3.2.38.x	Summary of Death	SAF	X	X	X		X	
3.2.39.x	Overall Summary of Treatment- Emergent Adverse Events by Age Group	SAF	X	X	X			

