3.2.60.x	Summary of Treatment-Emergent Adverse Events leading to Lenalidomide Dose Modification by MedDRA SOC and Preferred Term by Creatinine Clearance	SAF	X		X			
3.2.61.x	Summary of Treatment-Emergent Adverse Events Leading to Discontinuation of Lenalidomide by MedDRA SOC and Preferred Term by Creatinine Clearance	SAF	X		X			
3.2.62.x	Summary of Treatment-Emergent Adverse Events of Special Interest (eCRF) by Category, Preferred Term, and Maximum Severity by Creatinine Clearance	SAF	X		X			
3.2.63.x	Summary of Treatment-Emergent Adverse Events by MedDRA SOC and Preferred Term - Differences Between Japanese and Non-Japanese Participants	SAF			X			
3.2.64.x	Summary of Treatment-Emergent Adverse Events by MedDRA Preferred Term in Decreasing Order of Frequency Difference Between Japanese and Non- Japanese Participants	SAF			X			
3.2.65.x	Summary of Grade 3 or 4 Treatment- Emergent Adverse Events by MedDRA Preferred Term in Decreasing Order of Frequency Difference Between Japanese and Non-Japanese Participants	SAF			X			
3.2.66.x	Summary of Treatment-Emergent Adverse Events with a Fatal Outcome by MedDRA Preferred Term in Decreasing Order of Frequency Difference Between Japanese and Non-Japanese Participants	SAF			X			
3.2.67.x	Summary of Serious Treatment- Emergent Adverse Events by MedDRA Preferred Term in Decreasing Order of Frequency Difference Between Japanese and Non-Japanese Participants	SAF			X			

Table No.	Title	Pop	FL	MZL	Overall	Jap FL	Jap Overall	Standard
3.2.68.x	Summary of Treatment-Emergent Adverse Events Leading to Discontinuation of Study Drug by MedDRA Preferred Term in Decreasing Order of Frequency Difference Between Japanese and Non-Japanese Participants	SAF			X			
3.2.69.x	Summary of Treatment-Emergent Adverse Events Leading to Dose Modification of Tafasitamab/Placebo by MedDRA Preferred Term in Decreasing Order of Frequency Difference Between Japanese and Non-Japanese Participants	SAF			X			
3.2.70.x	Summary of Grade 3 or 4 Treatment- Emergent Adverse Events by MedDRA SOC, Preferred Term (Differences Between Japanese and Non-Japanese Participants)	SAF			X			
3.2.71.x	Summary of Grade 5 Treatment- Emergent Adverse Events by MedDRA SOC, Preferred Term (Differences Between Japanese and Non-Japanese Participants)	SAF			X			
3.2.72.x	Overall Summary of Treatment- Emergent Adverse Events by Age Group (<75 vs >= 75)	SAF	X	X	X			

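### SPM is followed beyond the 90-day AE window for some participants, but no planned by-arm table uses that later follow-up

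*SAP*

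**What the plan says.** **Collection.** Protocol 8.3 sets the general rule: "Adverse events, pregnancies, concomitant medications, procedures, and hospitalizations will be recorded from signing the ICF until 90 days after the last dose of treatment". Recording stops sooner if new anticancer therapy begins first. The same paragraph makes one exception. Participants who relapse or progress, and those who "prematurely discontinue the study treatment will continue to be followed for SPM throughout" the study, are followed for SPM beyond that limit. Protocol 9.2 classes every secondary malignancy as an SAE.

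**Status of SPM.** Protocol 9.5.1 and SAP 8.2.2 list SPM among the AESIs for tafasitamab/placebo. It is the only AESI named for lenalidomide: "Adverse events of special interest for lenalidomide include SPMs".

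**Analysis.** SAP 8.2.1 defines a TEAE as starting or worsening from first dose to 90 days after last dose, and then states: "Analysis of AEs (as discussed below) will be limited to TEAEs, but data listings will include all AEs regardless of their timing". The AESI sections, 8.2.2 and 8.2.3, follow that rule and make no exception for SPM. In Appendix A, Table 3.2.31 is titled "Summary of Treatment-Emergent Adverse Events of Special Interest (eCRF) by Category, Preferred Term, and Maximum Severity". Tables 3.2.32 to 3.2.34, and 3.2.62 by creatinine clearance, are likewise titled treatment-emergent.

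**The concern.** The protocol extends follow-up for this one event type, and the SAP plans no comparison that uses the extension. SPM can arise long after a treatment course of at most 12 cycles. Both arms receive lenalidomide, so only the randomized comparison can show whether adding tafasitamab changes the SPM rate. The possibility is not remote: Protocol 2.1.4.6 reports basal cell carcinoma as a second primary malignancy in 2 participants treated with tafasitamab plus lenalidomide in the single-arm DLBCL study. As planned, the arms are compared for SPM in the early period only. Later cases appear line by line, without a count by arm or a person-time denominator.

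**Working it through.** **Which rule governs a late SPM.** I looked for any route by which an SPM with a known onset date, more than 90 days after last dose, enters a by-arm SPM table.
- SAP 8.2.1 treats an AE as a TEAE unless it is unequivocally not one. That helps with uncertain dates, not with a dated late case.
- SAP 8.2.2 censors serious AESIs without an end date at cutoff, study discontinuation or death. That governs duration, not which onsets are counted.
- SAP 8.2.2 and the list in 8.2.4 say AESI without the words treatment-emergent, but 8.2.1 and the table titles settle the scope.
- The adverse-event tables run from 3.2.1 to 3.2.81 without a gap, and no other one covers SPM.
- A fatal case counts in overall survival and in the death summary. The three cause-of-death categories in SAP 7.3.2.3 do not identify SPM, and non-fatal cases are absent.

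No such route exists; late SPMs appear only in listings such as 2.7.1, 2.7.2 and 2.7.11.

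**The plan's own duration, reproduced.** Screening 28 + treatment 12 × 28 + follow-up 60 × 30.4375 = 2190 days, or 6.00 years. This matches the approximate 6-year maximum in Protocol 4.2.

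**One participant.**
- Twelve cycles: last lenalidomide dose on Cycle 12 Day 21 = 11 × 28 + 21 = day 329. The window closes at 329 + 90 = day 419. Possible observation is 336 + 1826 = 2162 days. Share outside = 1 − 419/2162 = 0.806. Taking Cycle 12 Day 28 as last dose gives 1 − 426/2162 = 0.803.
- Stopping after three cycles, with last dose taken as day 84: 1 − (84 + 90)/(84 + 1826) = 1 − 174/1910 = 0.909.

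**All participants.** Assume a constant SPM hazard and a constant monthly hazard *h* of leaving observation. With W = 419/30.4375 = 13.77 months and T = 2162/30.4375 = 71.03 months, the share of at-risk time outside the window at the final analysis is

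(e^(−hW) − e^(−hT)) / (1 − e^(−hT)), or 1 − W/T when h = 0.

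For the primary analysis, numerator and denominator are averaged over follow-up times uniform from 12.5 to 33.5 months (21 months of accrual, cutoff at 33.5 months, SAP 9.2.1). Follow-up time replaces T, and the numerator is zero when follow-up is shorter than W.

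The inputs are median OS 120 months (SAP Table 15) and planned median PFS 42.8 and 27.8 months (SAP Table 2). The 15% dropout is an overall share (448/0.85 = 527, against 528 planned), spread here as −ln(0.85)/33.5 = 0.00485 per month.

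| Exit from observation | h per month | Final | Primary |
|---|---|---|---|
| None | 0 | 0.806 | 0.403 |
| Death | 0.00578 | 0.773 | 0.385 |
| Death + dropout | 0.01063 | 0.743 | 0.369 |
| New therapy, median 42.8 | 0.01620 | 0.708 | 0.352 |
| Same + dropout | 0.02105 | 0.676 | 0.337 |
| New therapy, median 27.8 | 0.02493 | 0.650 | 0.326 |
| Same + dropout | 0.02978 | 0.618 | 0.312 |

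Last row at final: (0.664 − 0.121)/(1 − 0.121) = 0.618.

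The first three rows apply throughout-study SPM follow-up to everyone. The last four end collection at new anticancer therapy, with planned median PFS as an assumed proxy. If the hazard is not constant (no attrition, final analysis), 1 − (419/2162)^k gives 0.683 for Weibull shape k = 0.7 and 0.882 for k = 1.3.

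**Why an added table needs person-time.** If collection ended at new anticancer therapy, person-years per participant at the final analysis would be 3.52 in TGA and 2.77 in TGB (ratio 1.27), or 3.07 and 2.46 with dropout (1.25). At the primary analysis the ratio is 1.10. With equal hazards, an extended table giving only n and % would then count about 25–27% more SPMs in TGA at the final analysis.

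**The case against.** The SAP carries out the protocol faithfully. Protocol 10.4.2 uses the same 90-day window, tabulates TEAEs and lists all AEs whatever their timing, and the stated safety endpoint is TEAE incidence and severity. Protocol 8.3 prescribes follow-up but promises no by-arm summary. Late cases are listed, and the IDMC's safety review covers AESIs. SAP 8.1 and 8.2.4 allow listings in place of sparse tables, Appendix A describes its lists as guidelines, and SAP 3.2 permits additional follow-up analyses. The later data may also be weak: Protocol 9.4 does not oblige investigators to seek SAEs actively after EOT, and blinding lasts only until the primary analysis (Protocol 6.3).

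Most of this stands, and it limits the point to an improvement. It does not supply the comparison: permission to add an analysis is not a plan for one, and a listing gives neither a rate nor a denominator.

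Three stronger readings are tempting and are not supported.
- *The SAP contradicts the protocol, or SPM data are lost.* Neither is so: the analysis rules agree, and late cases are listed.
- *The planned tables are biased by longer PFS in TGA.* The 25–27% figure does not describe them. Their window is tied to last dose in both arms; the imbalance would arise only in an extended count table with collection ending at new therapy.
- *Protocol 8.3 and 9.4 conflict.* Section 9.4 carries SAE reporting to study completion or "until the participant starts a new anticancer therapy (whichever occurs earlier) must be reported to the sponsor", but allows for exceptions stated elsewhere in the protocol, and 8.3 may be one. Part of the follow-up text in Protocol 8.2 and 8.9.3 is redacted, so this is a query only.

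**Conclusion.** The point holds as a worthwhile, inexpensive improvement. The plan is consistent with its TEAE endpoint but makes no by-arm use of the SPM follow-up that Protocol 8.3 adds. Under the constant-hazard assumptions above, roughly 60–80% of at-risk time at the final analysis lies outside the tables. At the primary analysis the figure is about 30–40%, so the planned tables still cover the majority of at-risk time then.

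The upper part of the final-analysis range (74–81%) applies throughout-study follow-up to everyone, whereas 8.3 does not name participants who complete treatment without progression. The lower part (62–71%) uses planned PFS as a stand-in for time to new therapy, which the documents do not give. These are shares of observation time, not of cases. The documents give no SPM rate for this regimen, so no number of missed cases is claimed.

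**What to change.** Keep the TEAE tables. In SAP 8.2.2/8.2.3 and Appendix A, add one by-arm SPM summary over all available follow-up in the safety set: n, %, person-years and rate per 100 person-years. State that at-risk time ends at the earliest of death, withdrawal, data cutoff or the end of SPM collection. Person-time matters because counts alone could favour the arm observed for less time if collection ends at new anticancer therapy. Cumulative incidence with death as a competing event is optional.

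The cost is one extra table. Later cases may be passively reported, may arise after unblinding or other therapies, and can be included only as far as they were collected. The summary should therefore be labelled descriptive.

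Two side queries for the sponsor, not part of the defect:
- Which SPM collection period applies under Protocol 8.3 and 9.4, including for participants who complete treatment without progression?
- Does the reference listing under SAP 8.2.3 expand the SPM entry to the relevant malignancy terms?

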8.2.2. Adverse Events of Special Interest by eCRF

The number (%) of participants who had an AESI, the time to onset of each AESI, and the longest duration of each AESI will be summarized by treatment group.

Whether an AE is an AESI and which AESI it is can be found in the "Adverse Event" eCRF form. This information will be used to identify AESIs.

Adverse events of special interest for tafasitamab/placebo include TLS, IRRs and allergic reactions to study drug ≥ Grade 3, CRS, SPMs, hepatitis B reactivation, and PML.

Adverse events of special interest for lenalidomide include SPMs.

The longest duration of an AESI is defined as the longest interval between the date of occurrence of an AESI and the date of resolution. If participants have a missing or partial onset/end date of an AESI, the partial or missing dates will be handled using the rules explained in Section 4.1.4. Participants who have a missing end date of an AESI at the time of analysis will be right-censored using the following algorithm:

- If the AESI is serious, then the participant will be censored at the earlier date of data cutoff, study discontinuation, or death.
- If the AESI is not serious,
 - If the participant is ongoing with study treatment, then the participant will be censored at the data cutoff date.
 - If the participant discontinued treatment, then the participant will be censored at date of safety follow-up visit, or 90 days after the EOT visit (or after the last dose if the EOT visit was not performed), whichever is later; the censored date will be truncated by the earlier date of data cutoff, study discontinuation, or death if beyond.

The Kaplan-Meier estimate of median time to resolution/improvement and its 95% CIs will be provided, with the CIs calculated using the generalization of Brookmeyer and Crowley's method (1982) with log-log transformation (Klein and Moeschberger 1997). Resolution/improvement rates at selected timepoints will also be provided with 95% CIs calculated using Greenwood's formula to estimate the standard error. Such analysis for an AESI will not be conducted if 10 or fewer participants had the AESI.

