8.2.3. Adverse Events of Special Interest by Category and Preferred Term

A second method will also be used to identify AESIs programmatically using SMQs, custom MedDRA queries, and/or selected PTs.

Adverse events of special interest for tafasitamab/placebo include:

- Standard MedDRA Queries
 - Tumour lysis syndrome
 - Hypersensitivity (≥ Grade 3)
- Preferred terms
 - Cytokine release syndrome
 - Second primary malignancy
 - Hepatitis B reactivation

Progressive multifocal leukoencephalopathy

Adverse events of special interest for lenalidomide include:

- Preferred term
- Second primary malignancy

The analysis of the AESI by category and PT will be carried out as described in Section 8.2.2.

A listing will display the complete selected category and PTs from custom MedDRA queries and/or the selected PTs, defined by the sponsor. This will be used as reference listing.

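### The Kaplan-Meier time-to-resolution analysis of AESIs censors at death, so it overstates how often AESIs resolve when participants die with the event; the size depends on the AESI, and a fatal AESI could also be counted as resolved

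*SAP*

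**What the plan says.** SAP 8.2.2 defines the longest duration of an AESI as "the longest interval between the date of occurrence of an AESI and the date of resolution". Censoring is limited to one group: "Participants who have a missing end date of an AESI at the time of analysis will be right-censored using the following algorithm". For serious events, "If the AESI is serious, then the participant will be censored at the earlier date of data cutoff, study discontinuation, or death". For nonserious events after treatment discontinuation, death also ends follow-up: "the censored date will be truncated by the earlier date of data cutoff, study discontinuation, or death if beyond".

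The estimator is then fixed: "The Kaplan-Meier estimate of median time to resolution/improvement and its 95% CIs will be provided". "Resolution/improvement rates at selected timepoints will also be provided with 95% CIs", with standard errors by Greenwood's formula. There is a size threshold: "Such analysis for an AESI will not be conducted if 10 or fewer participants had the AESI". The text does not say whether the threshold applies per arm or in total.

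SAP 8.2.3 carries the method over to AESIs found by MedDRA terms: "The analysis of the AESI by category and PT will be carried out as described in Section 8.2.2". Two planned tables in SAP Appendix A are therefore affected, 3.2.32 and 3.2.34.

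Three other places matter:
- Protocol 9.2 makes every secondary malignancy an SAE, so the rule for serious events covers all second primary malignancies (SPMs).
- SAP 4.1.4, to which 8.2.2 refers for partial dates, sets a partial AE end date to the earlier of the end of the known month or year and the date of withdrawal or death.
- Protocol 9.3 records the event outcome, with fatal as a category separate from recovered.

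Neither document specifies a competing-risk method for this analysis.

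**The concern.** Kaplan-Meier censoring assumes that a censored participant could still have the event later. A participant who dies with an unresolved AESI cannot. Death is a competing event, and one minus the Kaplan-Meier curve then estimates resolution in a setting where nobody dies, not the proportion of participants who recover. The label on the output, a resolution rate, invites the second reading.

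At stake is the description of how reversible these events are. The AESI list includes SPM, progressive multifocal leukoencephalopathy and hepatitis B reactivation, where death with the event is a real possibility.

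A second gap works in the same direction. Because only missing end dates are censored, an event whose end date is entered or imputed as the date of death has an end date like any other. Nothing in SAP 8.2.2 stops it from being counted as resolved.

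**Working it through.** The SAP states no figure for this analysis, so there is none to reproduce.

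**Direction of the bias, without assumed hazards.** Take 12 participants. Four resolve at months 3, 9, 15 and 21. Four die unresolved at months 2, 6, 12 and 18. Four are alive and unresolved at month 24. The numbers at risk at the four resolutions are 11, 9, 7 and 5.
- Planned method: S(24) = (10/11)(8/9)(6/7)(4/5) = 1920/3465 = 0.554, so the reported rate is 44.6%.
- Actual proportion resolved: 4/12 = 33.3%.

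Without the four survivors, the numbers at risk are 7, 5, 3 and 1. The planned rate reaches 100%, although 4 of 8 (50%) resolved.

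**Size under constant hazards.** Let r be the monthly hazard of resolution and d that of death.
- Planned: 1 − exp(−rt)
- Cumulative incidence: r/(r+d) × [1 − exp(−(r+d)t)]

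*Planning mortality.* SAP 9.2.1 assumes a control median OS of 120 months, so d = ln 2/120 = 0.00578. Assume r = 0.10. At t = 24:
- planned 1 − exp(−2.4) = 90.9%
- cumulative incidence 0.10/0.10578 × [1 − exp(−2.539)] = 0.9454 × 0.921 = 87.1%
- excess about 4 points

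*Other assumed values*, with hazards set as ln 2 divided by the median:

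| Median to resolution / death (months) | Planned, 24 months | Cumulative incidence, 24 months | Excess (points) |
|---|---|---|---|
| 0.1 to 0.25 / 120 | 100% | 99.8–99.9% | 0.1–0.2 |
| 1 / 120 | 100% | 99.2% | 0.8 |
| 24 / 60 | 50% | 44.4% | 5.6 |
| 24 / 24 | 50% | 37.5% | 12.5 |
| 12 / 24 | 75% | 58.3% | 16.7 |
| 12 / 12 | 75% | 46.9% | 28.1 |

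The first two rows stand for acute events such as infusion reactions, cytokine release and tumor lysis. The last four are an assumed SPM-like range.

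*Median.* In the 12/24 row the planned median is 12 months. The cumulative incidence reaches one half when (2/3)(1 − 2^(−t/8)) = 0.5, that is at t = 16 months. In the 12/12 row its limit is r/(r+d) = 0.5, approached but not reached, so there is no finite median.

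**Would the SPM analysis run?** Protocol 2.1.4.6 reports, from the single-arm tafasitamab plus lenalidomide study in DLBCL, 2 participants with basal cell carcinoma and 1 with myelodysplastic syndrome. The denominator of 81 is inferred from 9 participants being 11.1%. The planned total is 618, or 309 per arm.
- Counting all three: 3/81 × 309 = 11.4, with a binomial chance of about 60% of exceeding 10. If the rate applied to all 618, the expected number is 22.9.
- Counting only the two that the protocol labels as SPM: 2/81 × 309 = 7.6, below the threshold.

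**End dates.** Suppose a participant dies in the same month as a partial AESI end date. SAP 4.1.4 compares the last day of that month with the date of death and takes the earlier, which is the date of death. The end date is then no longer missing, the censoring rule in 8.2.2 does not apply, and no condition on the outcome field is stated.

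**The case against.** **Fatal events are reported elsewhere.** A reader might infer that the method hides fatal AESIs. The documents do not support that. SAP 8.2.4 counts fatal TEAEs by arm, overall and by relation to each drug. SAP Appendix A plans AESIs by maximum severity (3.2.31 and 3.2.33), a summary of deaths (3.2.38) and listings of deaths and fatal adverse events. A rise in fatal AESIs would be visible in the report as a whole. This stands.

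**Censoring does not speed up the curve.** A reader might also infer that the arm with more deaths would appear to resolve faster. Under the model used here, the planned quantity 1 − exp(−rt) does not contain d, so more deaths leave it unchanged. The censoring fails to show the difference but does not reverse it. Apparent speeding-up would need informative censoring, for which there is no evidence here, or the end-date route.

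**The end-date route is a possibility, not a prediction.** The SAP measures to a date of resolution, and the eCRF separates fatal from recovered. What sites enter depends on completion guidelines that are not part of these documents. This stands for dates entered by sites. The partial-date rule, however, is in the SAP itself.

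**The hazards are assumed, and SPM may be a mild example.** Two of the three cases in the DLBCL study were basal cell carcinomas, and none of its three on-treatment deaths from adverse events was attributed to an SPM. SPMs enter this analysis only if they are treatment-emergent, up to 90 days after the last dose (SAP 8.2.1). This limits the size that can be claimed, not the direction.

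**No conclusion of the trial depends on it.** Safety output is descriptive, with no formal testing (SAP 8.1). This stands, and makes the point minor.

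**Conclusion.** The point holds as a minor one. As written, SAP 8.2.2 and 8.2.3 overstate the proportion of AESIs that resolve whenever a participant dies unresolved and others still at risk resolve later. The direction follows from the estimator. The size does not follow from the documents: the range from under 1 point for acute events to roughly 6 to 28 points for slow ones rests entirely on the assumed constant hazards, and the 4-point figure borrows trial-level planning mortality that may not apply after an AESI. Nor should equal hazards of resolution and death be read as meaning that fewer than half eventually resolve; under constant hazards the limit is exactly half.

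The output appears only for AESIs above the 10-participant threshold, which is possible but not certain for SPM. The end-date gap is a real omission, because the SAP can impute the date of death as an end date and has no rule on fatal outcomes.

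**What to change.** Amend SAP 8.2.2, which also covers 8.2.3 by reference:
1. Estimate the cumulative incidence of resolution with death as a competing event (Aalen-Johansen, with its own confidence intervals) in place of the Kaplan-Meier resolution rates and median.
2. State that an AESI is never counted as resolved if its outcome is fatal, or if its end date is recorded or imputed as the date of death without a resolved outcome.
3. Report by arm, at the selected timepoints, the proportions resolved, died unresolved and ongoing.

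The cost is a few sentences and a standard procedure. No new data are needed, because the outcome field is already collected, and efficacy, alpha and trial conduct are untouched. The downside is that the median is not estimable when the cumulative incidence stays below one half. The proportions in item 3 remain available in that case. The same edit could say whether the 10-participant threshold is per arm or in total.
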